7.3.4 Safety analyses

Safety will be analysed based on the assessments described in Section 2.2.2.2. All treated subjects (TS, refer to Section [7.2](#)) will be included in the safety analysis. Safety analyses will be descriptive in nature and based on BI standards. No hypothesis testing is planned.

For all analyses, the treatment actually administered (= treatment at onset) to the subject will be used (any deviations from the randomised treatment will be discussed in the minutes of the Report Planning Meeting).

Treatments will be compared in a descriptive way. Tabulations of frequencies/proportions will be used to evaluate categorical (qualitative) data, and tabulations of descriptive statistics will be used to analyse continuous (quantitative) data.

Measurements (such as ECG, vital signs, or laboratory parameters) or AEs will be assigned to treatments (see Section [4.1](#)) based on the actual treatment at the planned time of the measurement or on the recorded time of AE onset (concept of treatment emergent AEs). Therefore, measurements planned or AEs recorded prior to first intake of trial medication will be assigned to the screening period, those between first trial medication intake and end of REP (see Section [1.2.3](#)) will be assigned to the treatment period. Events occurring after the REP but prior to next intake or end of trial termination date will be assigned to 'follow-up'. In case of two or more treatments, the follow-up will be summarized according to the previous treatment. These assignments including the corresponding time intervals will be defined in detail in the TSAP. Note that AEs occurring after the last per protocol contact but entered before final database lock will be reported to Pharmacovigilance only and will not be captured in the trial database.

Additionally, further treatment intervals (analysing treatments) may be defined in the TSAP in order to provide summary statistics for time intervals, such as combined treatments, on-treatment totals, or periods without treatment effects (such as screening and follow-up intervals).

Adverse events will be coded using the Medical Dictionary for Regulatory Activities (MedDRA). Frequency, severity, and causal relationship of AEs will be tabulated by treatment, system organ class, and preferred term. SAEs, AESIs (see Section [5.2.5.1.4](#)), and other significant AEs (according to ICH E3) will be listed separately.

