## **6. GENERAL ANALYSIS DEFINITIONS**

### **6.1 TREATMENTS**

For basic study information on the treatment to be administered, and selection of dose, cf. Section 4 of the CTP.

Subjects will receive the following two treatments in a fixed sequence (reference treatment always followed by test treatment).

In Period Reference R, all subjects will receive 1 tablet containing

- 10 mg BI 425809 (Reference Treatment R) as a single dose

Afterwards, in Period Test T, all subjects will receive

- 2 capsules, each containing 200 mg Fluconazole, once daily for 13 days (Day -4 to Day 9) and 1 tablet containing 10 mg BI 425809 as a single dose on Day 1 (Test Treatment T).

For statistical analysis of AEs, the following analysis phases are defined for each subject.

Table 6.1: 1 Analysis phases for statistical analysis of AEs, and actual treatment for analysis of laboratory data and vital signs

Study analysis phase	Label	Start	End
Screening 	Screening	Date of informed consent	Date/time of first administration of BI 425809
On treatment	BI 425809	Date/time of first administration of BI 425809	Date/time of first administration of BI 425809 + REP (11 days) or 12:00 a.m. on day after last contact date (whichever occurs first)
Follow-up	F/U BI 425809	Date/time of first administration of BI 425809 + REP (11 days)	Date/time of first administration of Fluconazole or 12:00 a.m. on day after last contact date (whichever occurs first)
On treatment	Fluconazole	Date/time of first administration of Fluconazole	Date/time of second administration of BI 425809 or 12:00 a.m. on day after last contact date (whichever occurs first)
On treatment	BI + Fluconazole	Date/time of second administration of BI 425809	Date/time of second administration of BI 425809 + REP (14 days) or 12:00 a.m. on day after last contact date (whichever occurs first)
Follow-up	F/U BI + Fluconazole	Date/time of second administration of BI 425809 + REP (14 days)	12:00 a.m. on day after last contact date

 See [Section 6.7](#) for definition of baseline, which will be used in the statistical analyses of safety laboratory data and vital signs.

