The on-treatment phase for 'BI + Fluconazole' includes both the REP for BI 425809 (14 days) and Fluconazole (6 days). Since the second administration of BI 425809 is scheduled at 9:00 am on Visit 3, Day 1, while the last administration of Fluconazole is scheduled at 8:00 am on the Visit 3, Day 9 (see CTP, Flow chart). Therefore, Date/time of the second administration of BI 425809 + REP (14 days) is one hour after Date/time of the last administration of Fluconazole + REP (6 days).

AE summary tables will present results for the on-treatment phases only. All AEs will be listed.

In AE tables in CTR Section 15.3 (but not in Appendix 16.1.13.1.8.1 and Appendix 16.1.13.1.8.2 AE tables), the following totals will be provided in addition:

- **"Total BI"**, defined as the total over all on-treatment phases involving BI 425809
- **"Total Fluconazole"**, defined as the total over all on-treatment phases involving Fluconazole
- **"Total on-trt"**, defined as the total over all on-treatment phases

Safety laboratory data, vital signs and PK parameters will be analyzed based on treatment periods (BI 425809 and BI+Fluconazole) with clear differentiation between baseline (cf. [Section 6.7](#)) and post-baseline measurements. Measurements will be considered on-treatment, if they were taken within the on-treatment phases of BI 425809 or BI+Fluconazole as defined in [Table 6.1: 1](#). More details on the technical implementation of these analyses are provided in the ADS Plan of this TSAP.

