### 7.8.1 Adverse Events

AEs will be coded with the most recent version of MedDRA.

The analyses of AEs will be descriptive in nature. All analyses of AEs will be based on the number of subjects with AEs and not on the number of AEs.

For further details on summarization of AE data, please refer to “Analysis and Presentation of Adverse Event Data from Clinical Trials” [\(7\)](#) and “Handling of missing and incomplete AE dates” [\(3\)](#).

The analysis of AEs will be based on the concept of treatment emergent AEs. That means that all AEs will be assigned to screening, on-treatment or follow-up phases as defined in [Section 6.1](#). AEs will be analysed based on actual treatments, as defined in [Table 6.1: 1](#).

An overall summary of AEs will be presented. This overall summary will comprise summary statistics for the class of AESIs.

**CTP:** *Hepatic injury is considered an AESI in this trial. A hepatic injury is defined by the following alterations of hepatic laboratory parameters:*

- *An elevation of AST (aspartate transaminase) and/or ALT (alanine transaminase)  $\geq 3$  fold ULN combined with an elevation of total bilirubin  $\geq 2$  fold ULN measured in the same blood sample, or*
- *Aminotransferase (ALT, and/or AST) elevations  $\geq 10$  fold ULN*

The investigator had to classify on the eCRF whether an observed AE was an AESI or not.

According to ICH E3 (8), in addition to Deaths and Serious Adverse Events, ‘other significant’ AEs need to be listed in the clinical trial report. These will be any non-serious adverse event that led to an action taken with study drug (e.g. discontinuation or dose reduced or interrupted).

The frequency of subjects with AEs will be summarised by treatment, primary SOC and preferred term. AEs which were considered by the investigator to be drug related will be summarised separately. Separate tables will also be provided for subjects with SAEs and subjects with AESIs. AEs will also be summarized by maximum intensity.

The SOC and preferred terms within SOC will be sorted by descending frequency.

For disclosure of AE data on ClinicalTrials.gov, the frequency of subjects with non-serious AEs occurring with an incidence of greater than 5 % (in preferred terms) will be summarised by primary SOC and preferred term. The frequency of subjects with SAEs will also be summarised.

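### AE percentages for Reference, Test and fluconazole alone come from phases of 11, 14 and about 4 days, so the descriptive comparison is not like for like

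*SAP*

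**What the plan says.** SAP 6.1, Table 6.1: 1, defines the phases to which AEs are assigned. The Reference phase starts at the first BI 425809 dose and ends at "Date/time of first administration of BI 425809 + REP (11 days". The Test phase starts at the second BI 425809 dose and ends at "Date/time of second administration of BI 425809 + REP (14 days". Both are cut at last contact if that comes earlier. The fluconazole-alone phase runs from the first fluconazole dose to the second BI 425809 dose, which the protocol's Flow Chart puts 97 h apart.

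The text below the table gives the reason for the 14 days: the phase covers a 14-day residual effect period (REP) for BI 425809 and a 6-day REP for fluconazole. The same text says "AE summary tables will present results for the on-treatment phases only" and adds pooled totals, among them one over all phases that involve fluconazole.

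SAP 7.8.1 fixes the counting unit: "All analyses of AEs will be based on the number of subjects with AEs and not on the number of AEs". It fixes the layout too: "The frequency of subjects with AEs will be summarised by treatment, primary SOC and preferred term". SAP 7 expresses frequencies as percentages of the treatment group. SAP 7.7 plans descriptive exposure statistics but does not link them to AEs.

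Protocol 7.3.4 states the purpose: "Treatments will be compared in a descriptive way". It adds "No hypothesis testing is planned", and it allows the SAP to define further treatment intervals.

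**The concern.** The percentage of subjects with at least one AE rises with the length of time counted. Setting an 11-day, a 14-day and a 4-day column side by side therefore mixes any drug effect with the time at risk. A reader of the AE tables would naturally set Test against Reference to see what fluconazole adds, and Test against fluconazole alone to see what the combination adds. Part of either difference could come from window length. ECG findings have no separate analysis (SAP 7.8.4) and appear only as AEs, so the AE tables are also where an ECG signal would be read.

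What is at stake is the reading of a descriptive safety table. No hypothesis test and no PK endpoint depends on it.

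**Working it through.** **1. The plan's own figure.** SAP 6.1 says the 14-day BI 425809 window ends one hour after the 6-day fluconazole REP. Day 1 at 09:00 plus 14 days is Day 15 at 09:00. Day 9 at 08:00 plus 6 days is Day 15 at 08:00. The difference is 1 h, as stated.

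**2. Window lengths.** Reference is 11 × 24 = 264 h, Test is 14 × 24 = 336 h, and fluconazole alone is 97 h = 97/24 = 4.04 days. Test/Reference = 14/11 = 1.27. For completers the schedule shortens neither long window:
- Reference: with the minimum 16-day wash-out, first fluconazole comes at 16 × 24 − 97 = 287 h, after 264 h.
- Test: the end-of-trial visit is on Day 16 at the earliest, after the window closes on Day 15.

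**3. Expected size with no drug effect.** The documents give no background AE incidence, so it is varied. Assume a constant hazard, equal in both periods, and full recall. If a proportion p has an AE in 11 days, the proportion in t days is 1 − (1 − p)^(t/11).

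| Reference, 11 d | Test, 14 d | Gap, points | Gap, of 15 subjects | Ratio | Fluconazole alone, 97 h |
|---|---|---|---|---|---|
| 5% | 6.3% | 1.3 | 0.20 | 1.26 | 1.9% |
| 20% | 24.7% | 4.7 | 0.71 | 1.24 | 7.9% |
| 30% | 36.5% | 6.5 | 0.97 | 1.22 | 12.3% |
| 50% | 58.6% | 8.6 | 1.29 | 1.17 | 22.5% |
| 60% | 68.8% | 8.8 | 1.33 | 1.15 | 28.6% |

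The ratio approaches its ceiling of 14/11 = 1.27 as p falls towards zero. The largest absolute gap is 8.9 points (1.33 of 15 subjects), at a Reference incidence of about 59%. The pooled fluconazole total spans 4.04 + 14 = 18.04 days. At 30% under Reference it would show 44.3%, and its ratio to Reference can reach 18.04/11 = 1.64.

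**4. What one trial of 15 would show.** With independent binomial counts and a Reference incidence of 20% to 60%, Test has the higher count with probability 0.54 to 0.63, ties with 0.13 to 0.17, and is lower with 0.24 to 0.30. At 5% these are 0.39, 0.34 and 0.27. A simulation in which some subjects are more AE-prone than others in both periods (Reference 30% or 50%) gives a gap of about 4 to 6 points and a probability of 0.53 to 0.57 that Test is higher.

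**5. Late time in each window.** In both periods the last scheduled contact inside the window is at 215 h. The time after it is (264 − 215)/264 = 19% of the Reference window and (336 − 215)/336 = 36% of the Test window. Active questioning about it happens only at the next visit: the first fluconazole visit for Reference, and the Day 16 to 30 visit for Test. If nothing after 215 h were recalled, the two effective windows would be equal and the window-length gap would vanish.

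**The case against.** The strongest defence is that the windows follow a stated rule. AEs are assigned by residual effect period, and a longer period under co-administration is part of the treatment being described. That stands: the 14-day window is not a mistake. The REP derivation in Protocol 1.2.3 is redacted, so it cannot be challenged here.

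Several other points also stand. Safety is a further objective, assessed descriptively in 15 subjects. All AEs are listed, onset times are recorded, and the window lengths are printed in the SAP, so a careful reader could make the restriction unaided. Further AE summary detail sits in an internal standard that is not available here and might add something.

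A reader might infer more than the documents support:
- That Test will show more AEs even without a drug effect. This is only a tendency, and it concerns subjects with AEs, not events. By the figures above, Test is not higher in roughly 4 of 10 trials at 20% to 60% incidence, and in about 6 of 10 at 5%.
- That the fixed sequence causes or worsens the problem. Window length belongs to the treatment, so a randomised sequence would give Test the same 14 days.
- That AEs per subject-day would settle it. Such a rate assumes a constant hazard. If AEs cluster early, Test's longer quiet tail would dilute its rate.

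What the defence does not answer is that the visible plan promises a treatment comparison and contains no table on equal time.

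**Conclusion.** The point holds as a modest weakness in presentation. The three on-treatment phases differ in length, the AE summaries are crude percentages of subjects, and the visible text makes no allowance for time. With no drug effect, the expected Test/Reference ratio lies above 1 and does not exceed 1.27, and the gap is at most about 9 percentage points. The fluconazole-alone percentage is biased downwards against both other columns.

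These figures rest on a constant background hazard equal in both periods and on full recall, neither of which the documents establish. Clustering of AEs near dosing or poor recall of late AEs would shrink the gap, and a period effect could move it either way. Importance is low, and the primary PK conclusions are unaffected.

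**What to change.** Keep the REP-based tables as they are and make two additions in SAP 7.8.1.

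1. Add one summary of subjects with AEs by treatment over 0 to 215 h after each BI 425809 dose. Both periods have a scheduled contact at 215 h, and Protocol 7.3.4 already permits the extra interval.
2. Show each phase's length in the AE table headers, with a note that crude percentages from phases of different length are not directly comparable.

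The cost is one table, a header change and a sentence, with no new data. There are two limits to state:
- AEs after 215 h fall outside the added table, although they stay in the REP tables. This includes most of the fluconazole REP: the last dose is at 191 h, so only 24 of its 144 h lie inside.
- The common window equalises time but not questioning. Test subjects are asked about AEs on Days 5, 7 and 9, when Reference subjects are not.

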			7:00	16:00	Light snack (voluntary)						
			8:00	17:00			x				x
			10:00	19:00	Dinner						
			12:00	21:00			x				x
		2	23:00	08:00	Fluconazole administration			x ⁷			x
			24:00	09:00	Breakfast (voluntary) ³ , discharge from trial site	B	x		x	x	x
		3	47:00	08:00	Fluconazole administration ⁶		x	x			x
		4	71:00	08:00	Fluconazole administration ⁶	C	x				x
		5	95:00	08:00	Fluconazole administration						x
		6	119:00	08:00	Fluconazole administration ⁶	C	x				x
		7	143:00	08:00	Fluconazole administration						x
		8	167:00	08:00	Fluconazole administration ⁶	C	x		x		x
		9	191:00	08:00	Fluconazole administration						x
		10	215:00	08:00	Ambulatory visit		x				x
FU	4	16 to 30			End of trial (EoTrial) examination ⁴	D			x	x	x

1. See [Flow Chart](#) on previous page.
2. The time is approximate; the procedure is to be performed and completed within the 2 h prior to fluconazole drug administration.
3. If several actions are indicated at the same time, the intake of meals will be the last action.
4. At the end of trial visit the EoTrial examination includes physical examination, vital signs, ECG, safety laboratory, recording of AEs and concomitant therapies.
5. AEs and concomitant therapies will be recorded throughout the trial, but will be specifically asked for at the times indicated in the Flow Chart above.
6. Immediately after PK blood sampling.
7. PK sampling pre-dose (tolerance with respect to planned time: -5 min); fluconazole administration on time.
8. Letters A, B, C and D define different sets of safety laboratory examinations (for details refer to Section [5.2.3](#)).
9. Including urine drug screening and alcohol breath test

TABLE OF CONTENTS

TITLE PAGE	1
CLINICAL TRIAL PROTOCOL SYNOPSIS	2
FLOW CHART	4
TABLE OF CONTENTS	6
ABBREVIATIONS	10
1. INTRODUCTION.....	13
1.1 MEDICAL BACKGROUND	13
1.2 DRUG PROFILE	13
1.2.1 BI 425809	13
1.2.1.1 Non-clinical drug safety.....	13
1.2.1.2 Clinical Safety in Healthy Subjects	14
1.2.1.3 Expected exposure of BI 425809 in this trial.....	15
1.2.2 Fluconazole	16
1.2.3 Residual Effect Period	19
1.3 RATIONALE FOR PERFORMING THE TRIAL	19
1.4 BENEFIT - RISK ASSESSMENT	19
1.4.1 Expected benefit for the target population	19
1.4.2 Procedure-related risks	20
1.4.3 Drug-related risks and safety measures.....	20
1.4.3.1 Risks related to the administration of BI 425809	20
1.4.3.2 Risks related to the administration of fluconazole.....	21
1.4.3.3 Drug-induced liver injury	22

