#### **4. CHANGES IN THE PLANNED ANALYSIS OF THE STUDY**

All analyses described in this TSAP are in accordance with the statistical methods described in the CTP.

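### The SAP keeps adverse events with onset after the residual effect period out of every AE, SAE and AESI summary table, although the protocol says follow-up will be summarised and the SAP declares no departure

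*SAP*

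**What the plan says.** **Protocol, section 7.3.4 (Safety analyses).** AEs are assigned "based on the actual treatment at the planned time of the measurement or on the recorded time of AE onset". Events after the residual effect period (REP) go to follow-up, and the protocol continues: "In case of two or more treatments, the follow-up will be summarized according to the previous treatment". On detail it adds: "These assignments including the corresponding time intervals will be defined in detail in the TSAP". It also allows the SAP to define additional intervals for summary statistics, including "periods without treatment effects (such as screening and follow-up intervals"). SAEs, AESIs and other significant AEs are to be listed separately.

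**SAP, section 6.1 and Table 6.1: 1.** Six phases are defined: screening, three on-treatment phases and two follow-up phases, labelled F/U BI 425809 and F/U BI + Fluconazole. The text then says: "AE summary tables will present results for the on-treatment phases only. All AEs will be listed". The three added totals are also built from on-treatment phases only.

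**SAP, section 7.8.1.** Overall, drug-related, SAE, AESI and maximum-intensity summaries are planned. None is exempted from the on-treatment restriction.

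**SAP, section 4.** "All analyses described in this TSAP are in accordance with the statistical methods described in the CTP".

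**The concern.** The SAP derives two follow-up phases, each labelled by the preceding treatment, and then uses neither in any AE table it describes. The protocol's sentence on follow-up has no counterpart in the planned tables, and the SAP does not acknowledge the difference.

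The schedule gives this practical weight. Hepatic injury is the only AESI, and one of its two definitions needs raised AST or ALT together with raised total bilirubin in the same blood sample. If the scheduled sample best placed to meet that definition falls after the on-treatment cut-off, the AESI table can show zero while a listing shows a case. Readers of a trial report usually take SAE and AESI counts from the summary tables.

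**Working it through.** No sample size, power or alpha figure bears on this point. The check is clock arithmetic plus a reading of the assessment schedule, using nominal flow-chart times.

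**1. The SAP's own figure.** Count hours from the second BI 425809 dose (Day 1, 09:00), so that Day d at clock hour h is (d − 1) × 24 + h − 9.
- End of the BI + Fluconazole phase: 14 × 24 = 336 h, which is Day 15, 09:00.
- Last fluconazole dose (Day 9, 08:00): 8 × 24 + 8 − 9 = 191 h. Adding 6 days gives 191 + 144 = 335 h.
- Difference: 336 − 335 = 1 h. This agrees with the one hour stated in SAP section 6.1.

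**2. The end-of-trial visit in completers (Flow Chart: Day 16 to 30).**
- Start of Day 16: 15 × 24 − 9 = 351 h, which is 351 − 336 = 15 h after the cut-off.
- End of Day 30: 29 × 24 + 24 − 9 = 711 h, which is 711 − 336 = 375 h (15.6 days) after it.
- With a visit at 08:00 (assumed for illustration), the time since the last fluconazole dose is 359 − 191 = 168 h (7 days) on Day 16 and 695 − 191 = 504 h (21 days) on Day 30.

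Every on-schedule end-of-trial visit of a completer is therefore after the cut-off.

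**3. What that visit measures (Flow Chart for Treatment T and protocol Table 5.2.3: 1).**

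| Day | Laboratory set | AST/ALT | Total bilirubin |
|---|---|---|---|
| −1 | C | yes | no |
| 1 | B | yes | yes |
| 2 | B | yes | yes |
| 4, 6, 8 | C | yes | no |
| 10 | none | no | no |
| 16 to 30 | D | yes | yes |

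The last scheduled liver panel before the cut-off is on Day 8, before the final fluconazole dose on Day 9. The first one after that dose is at end of trial. After Day 2, the end-of-trial sample is also the first scheduled one that contains both components of the combined AESI definition. The other definition, AST or ALT at least 10-fold above the upper limit of normal, can be met from set C.

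**4. What is still tabulated.** Assignment follows recorded onset. From the Day 10 visit at 08:00 (215 h) to the cut-off is 336 − 215 = 121 h. An AE starting in those 121 h is on-treatment even if first reported at end of trial. For an 08:00 visit, that is 121/144 = 84% of the time since Day 10 if the visit is on Day 16, and 121/480 = 25% if it is on Day 30.

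**5. The follow-up between periods.** With the minimum 16-day wash-out, an 11-day REP and the first fluconazole dose 97 h before the second BI 425809 dose, F/U BI 425809 lasts at least 384 − 264 − 97 = 23 h. AEs with onset there are also left out of the tables.

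**6. Other outputs.** The laboratory shift tables use the last value on treatment (SAP section 7.8.2), so they also omit a completer's end-of-trial sample. ECG and physical examination findings have no separate listing or analysis (SAP sections 7.8.4 and 7.8.5.1) and are reported after dosing only as AEs.

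**The case against.** The best defence is that the protocol sentence is an attribution rule. It sits in a paragraph about assigning events to intervals, the next sentence leaves the detail to the SAP, and follow-up appears again among intervals that may be defined. On that reading the labels in Table 6.1: 1 satisfy the protocol, and on-treatment tables fit its treatment-emergent concept. This softens the conflict but does not remove it. The delegation covers assignments and time intervals, and the optional sentence concerns additional intervals. Neither withdraws an unconditional statement that follow-up will be summarised. If the sponsor reads it otherwise, section 4 of the SAP is the place to say so.

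Three stronger readings are tempting and are not supported:
- *Anything first found at the end-of-trial visit escapes the tables.* Onset decides, not the visit of detection (step 4 above).
- *The end-of-trial visit is after the REP for everyone.* Under protocol section 3.3.4, subjects who discontinue are examined at discontinuation if possible, which can fall inside a REP. If the second BI 425809 dose is never given, the on-treatment Fluconazole phase runs to the day after last contact and so contains the visit.
- *Late events vanish from the report, or go unasked about after dosing.* All AEs are listed, SAEs and AESIs are listed separately, and possibly clinically significant laboratory values are listed in Section 15.4.1 of the report. Laboratory statistics over time are not expressly confined to on-treatment values. Day 10 also has AE questioning within the on-treatment phase. With 15 subjects, a careful reader would probably find a late case.

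**Conclusion.** The inconsistency is real and should be corrected, but it is a reporting gap and not a loss of data. It affects AEs with recorded onset after the REP: after Day 15, 09:00 in the test period, and between the end of the 11-day REP and the first fluconazole dose after the reference period. Two of the five post-dose phases in Table 6.1: 1 appear in no AE summary table.

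The consequence is a possible understatement in the overall AE, SAE and AESI counts. For completers, a combined transaminase and bilirubin AESI dated to the end-of-trial visit would be absent from the AESI table. One subject is 1/15 = 6.7%. The documents give no rate of onset after the REP, so no expected number of omitted events can be stated. The pharmacokinetic analyses are unaffected.

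This rests on nominal clock times, on 15 treated subjects, on findings at the end-of-trial visit being given that visit's date as onset, and on no unscheduled sample having shown the abnormality earlier.

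**What to change.** In SAP sections 6.1 and 7.8.1, replace the on-treatment-only restriction. Add the F/U BI 425809 and F/U BI + Fluconazole phases as separate columns, attributed to the preceding treatment, at least in the overall AE summary and the SAE and AESI tables. Extending them to the table by system organ class and preferred term is optional. Keep the on-treatment columns and the three totals unchanged.

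If the sponsor prefers on-treatment tables only, SAP section 4 should declare and justify the departure. That would settle the conflict between the documents but leave the AESI count incomplete, so the added columns are the better choice.

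The cost is a wording change and two columns for phases that are already defined, with no new data. The tables become slightly wider and include events outside the treatment-emergent window, shown separately so that they are not mixed with on-treatment counts.
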